## 2.0 TRIAL DESIGN

### 2.1 Trial Design

This is a randomized single-institution, phase II, open-label clinical trial of neoadjuvant pembrolizumab with or without low-dose stereotactic radiation therapy (SRT) in stage I- IIIA non-small lung cancer (NSCLC) patients who are planned to undergo surgical resection of their lung cancer.

Two consecutive run-in cohorts will administer pembrolizumab or pembrolizumab with SRT of 12 Gy to the lateral aspect of the primary tumor. Patients will receive pembrolizumab for 2 cycles prior to surgery or SRT and surgery. Surgical resection of all involved areas of tumor will occur within 6 weeks of the last administration of pembrolizumab. It should be noted that in almost all cases, surgery is expected to occur very expeditiously, within a much shorter window and 6 weeks would represent only the greatest allowable amount of delay.

If during the run-in, only the pembrolizumab-alone cohort meets pre-specified safety parameters, subsequently enrolled patients will enter a larger expansion cohort, with treatment given according to that cohort only. If during the run-in both cohorts meet pre-specified safety parameters, subsequently enrolled patients will enter the expansion cohort and be randomized between preoperative pembrolizumab versus pembrolizumab with SRT of 12 Gy.

Patients will be followed every 12 weeks for 1 year for disease status and survival.

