### 2.2 Trial Diagram

Two consecutive run-in cohorts will be treated establishing the safety of neoadjuvant pembrolizumab and pembrolizumab-SRT delivered in the preoperative window. An expansion cohort will include a larger number of patients who will be treated with pembrolizumab alone or be randomized between the two arms.

**Cohort 1:** 6 patients. The patients will undergo 2 cycles of pembrolizumab prior to surgery. Surgery will occur no later than 6 weeks following the last dose of pembrolizumab.

If  $\leq 33\%$  of patients experience grade 3 immune-related toxicity attributable to study interventions (as determined within 30 days of date of surgery), or  $\leq 1$  patient progresses to unresectability over the course of study treatment, proceed to Cohort 2.

If  $>33\%$  of patients experience grade 3 immune-related toxicity attributable to study interventions (as determined within 30 days of date of surgery), or  $> 1$  patient progresses to unresectability over the course of study treatment, the study will terminate.

**Cohort 2:** 6 patients. The patients will undergo 2 cycles of pembrolizumab then within the week (7 days  $\pm$  3 days) following administration of the second cycle, a single fraction of SRT (12 Gy) will be delivered to 50% of the primary tumor only. Definitive surgical resection will occur

[figure not shown]
no later than 6 weeks following the last dose of pembrolizumab.

If  $\leq 33\%$  of patients experience grade 3 immune-related toxicity attributable to study interventions (as determined within 30 days of date of surgery), or  $\leq 1$  patient progresses to unresectability over the course of study treatment, proceed to Expansion Cohort (randomization between parameters of Cohort 1 and Cohort 2, e.g. randomization between preoperative pembrolizumab versus pembrolizumab and SRT).

If >33% of patients in Cohort 2 experience grade 3 immune-related toxicity attributable to study interventions (as determined within 30 days of date of surgery), or > 1 patient progresses to unresectability over the course of study treatment, then proceed to Expansion Cohort (parameters only of Cohort 1, e.g. preoperative pembrolizumab alone).

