**Expansion Cohort:** 28 patients. The patients will be treated according to Cohort 1 if Cohort 2 failed to meet the specified safety milestones. If both cohorts met the safety milestones, then patients in this cohort will be randomized to parameters of either Cohort 1 or Cohort 2. Surgery will occur no later than 6 weeks following the last dose of pembrolizumab.

**Stopping Rule:** If at any point during the study, >15% of patients progress to unresectability over the course of the study treatment, then the study will terminate. This stopping rule will be cumulatively evaluated at all timepoints during the protocol, for all patients enrolled in any phase of the protocol. Each case of study-induced medical unfitness, tumor progression, or any other cause resulting in unresectability will trigger a re-evaluation of the 15% stopping rule.

\* Cycle 2 of pembrolizumab should be given except as recommended per protocol, section 5.2.1.2

\*\* SRT is delivered within 7 days +/- 3 days of second pembrolizumab cycle. If second cycle is not given due to discontinuation, SRT should not be given (patient should continue to surgery)

when deemed safe by treating surgeon).

^ Surgery will take place no later than 6 weeks following last dose of pembrolizumab, e.g. no later than week 7 if only one cycle of pembrolizumab was tolerated, or if two cycles of pembrolizumab were given, week 10.

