##### 5.2.1.1 Dose Modification (Escalation/Titration/Other)

Adverse events (both non-serious and serious) associated with pembrolizumab exposure, including coadministration with additional compounds, may represent an immunologic etiology. These adverse events may occur shortly after the first dose or several months after the last dose of pembrolizumab/combination and may affect more than one body system simultaneously. Pembrolizumab/combination treatment must be withheld for drug-related toxicities and severe or life-threatening AEs as per Table 3 below. See Section 5.6 for supportive care guidelines, including use of corticosteroids.

If a patient continues to experience toxicity, or if dosing with study drug is interrupted for > 14 consecutive days due to toxicity, treatment should be discontinued unless otherwise agreed between the investigators before reintroduction of study drug.

The following dose modification rules will be used with respect to potential toxicity. Toxicity will be assessed according to the NCI Common Terminology Criteria for Adverse Events [Version 4.0 \(CTCAE v4.0\)](#).

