	Is a new cancer (that is not a condition of the study) (although not serious per ICH definition, is reportable to the Principal Investigator within 24 hours and to Merck within 2 working days to meet certain local requirements); or	
	Is an overdose (whether accidental or intentional). Any adverse event associated with an overdose is considered a serious adverse event for collection purposes. An overdose that is not associated with an adverse event is considered a non-serious event of clinical interest and must be reported within 24 hours to the Principal Investigator and to Merck within 2 working days.	
	Other important medical events that may not result in death, not be life threatening, or not require hospitalization may be considered a serious adverse event when, based upon appropriate medical judgment, the event may jeopardize the subject and may require medical or surgical intervention to prevent one of the outcomes listed previously (designated above by a †).	
Duration	Record the start and stop dates of the adverse event. If less than 1 day, indicate the appropriate length of time and units	
Action taken	Did the adverse event cause Merck product to be discontinued?	

Relationship to Merck Product	Did Merck product cause the adverse event? The determination of the likelihood that Merck product caused the adverse event will be provided by an investigator who is a qualified physician. The investigator's signed/dated initials on the source document or worksheet that supports the causality noted on the AE form, ensures that a medically qualified assessment of causality was done. This initialed document must be retained for the required regulatory time frame. The criteria below are intended as reference guidelines to assist the investigator in assessing the likelihood of a relationship between the test drug and the adverse event based upon the available information. The following components are to be used to assess the relationship between Merck product and the AE; the greater the correlation with the components and their respective elements (in number and/or intensity), the more likely Merck product caused the adverse event (AE):
Exposure	Is there evidence that the subject was actually exposed to Merck product such as: reliable history, acceptable compliance assessment (pill count, diary, etc.), expected pharmacologic effect, or measurement of drug/metabolite in bodily specimen?

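### The Cohort 2 adverse branch charges toxicity that began before SRT to the combination and opens a 28-patient pembrolizumab-alone expansion, with no numeric rule that brings those events into the pembrolizumab-alone decision

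*Combined protocol and SAP*

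**What the plan says.** Section 2.2 (Trial Diagram) runs two six-patient cohorts in sequence and judges both against the same 33% toxicity limit, assessed within 30 days of surgery.

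- **Cohort 1 (pembrolizumab alone).** The adverse branch joins more than 33% toxicity, by an or, to the condition that more than one "patient progresses to unresectability over the course of study treatment, the study will terminate".
- **Cohort 2 (pembrolizumab, then SRT).** The trigger is "If >33% of patients in Cohort 2 experience grade 3 immune-related toxicity attributable to study interventions", again joined by an or to unresectability. The action is "then proceed to Expansion Cohort (parameters only of Cohort 1, e.g. preoperative pembrolizumab alone").
- **Same routing elsewhere.** Section 2.1 has "If during the run-in, only the pembrolizumab-alone cohort meets pre-specified safety parameters, subsequently enrolled patients will enter a larger expansion cohort", treated as that cohort was. The Expansion Cohort paragraph of 2.2 gives its size as 28.

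Four other provisions bear on the point:

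- **SRT timing.** Section 5.2 places the single fraction 7 days (+/- 3) after the second pembrolizumab dose and omits it if that dose is not given.
- **Attribution.** Section 5.2.1.1 lets the investigator attribute an event to the combination, to radiotherapy, or to pembrolizumab alone. It also says of the drug: "Adverse events (both non-serious and serious) associated with pembrolizumab exposure, including coadministration with additional compounds, may represent an immunologic etiology".
- **Replacement.** Under 5.9, a patient who leaves before surgery is replaced only if there was no grade 3 or higher toxicity.
- **Pooling.** The one cumulative rule, in 2.2, concerns unresectability above 15%: "This stopping rule will be cumulatively evaluated at all timepoints during the protocol, for all patients enrolled in any phase of the protocol". Toxicity has no counterpart.

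**The concern.** Every Cohort 2 patient first has about four weeks of exactly the Cohort 1 treatment. An event that begins in that window cannot be due to SRT. A patient whose early toxicity cancels the second dose never receives SRT, yet still counts in Cohort 2 and, if the toxicity is grade 3 or higher, is not replaced.

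The branch nevertheless reads the whole Cohort 2 count as a result for the combination. Its remedy is to remove SRT and continue the component those patients had actually received. The decision to open the pembrolizumab-alone expansion then rests on six Cohort 1 patients, and any contrary pembrolizumab evidence from Cohort 2 plays no numeric part in it. At stake is whether 28 further patients start a regimen on half of the relevant run-in evidence. The issue is the branch decision itself, before any expansion patient is treated.

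**Working it through.** **Inputs from the documents.** Run-in cohorts of 6 and 6 and a fixed total of 40 (7.2), so the expansion is 40 - 6 - 6 = 28, as stated. Limit 33% (2.2). SRT at nominal day 21 + 7 = 28, or 25 to 31 with the SRT window (5.2, 5.2.2). Grade 3 or higher adverse event rate in the cited advanced-disease trial: 47/495 = 9.5% (4.1.2); this is a stand-in, not a rate for grade 3 immune-related events before surgery.

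**Assumptions, not in the documents.** The two cohorts share one true toxicity rate p. SRT adds nothing. A share s of Cohort 2 events begins before SRT. The 33% limit is applied to all 12 run-in patients.

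**Two readings of the limit.** Since 2/6 = 33.3%:
- Strict 33%: a cohort passes with at most 1/6 and fails from 2/6; the 12-patient count is over from 4/12.
- One third: a cohort passes with at most 2/6 and fails from 3/6; the 12-patient count is over from 5/12.

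**Step 1: can it happen?** Take Cohort 1 at 1/6 (passes under both readings) and Cohort 2 at 4/6, all before SRT (fails under both). Pembrolizumab-alone experience is (1 + 4)/12 = 41.7%, exact 95% CI 15.2% to 72.3%. The branch still says proceed.

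**Step 2: does it happen in every Cohort 2 failure?** No. Even with all events before SRT, the 12-patient count is not over for 0+2, 0+3 or 1+2 events (16.7%, 25.0%, 25.0%) on the strict reading, or for 0+3, 0+4 or 1+3 (25.0%, 33.3%, 33.3%) on the one-third reading.

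**Step 3: how likely is it?** With X1 and X2 binomial(6, p) and K binomial(X2, s), the probability is P(X1 passes, X2 fails, X1 + K over the limit).

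At p = 0.40 and s = 1:
- Strict: P(X1=0)P(X2>=4) + P(X1=1)P(X2>=3) = 0.0467 x 0.1792 + 0.1866 x 0.4557 = 0.0084 + 0.0850 = 0.093.
- One third: 0.0467 x 0.0410 + 0.1866 x 0.1792 + 0.3110 x 0.4557 = 0.0019 + 0.0334 + 0.1417 = 0.177.

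| True rate p | Share before SRT | Strict | One third |
|---|---|---|---|
| 9.5% | all | 0.5% | 0.2% |
| 20% | all | 4.3% | 3.1% |
| 33% | all | 9.2% | 13.1% |
| 40% | all | 9.3% | 17.7% |
| 40% | half | 1.9% | 3.4% |
| 40% | 30% | 0.5% | 0.9% |

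The 30% row comes from the longest toxicity window: 21 days to dose 2, up to 42 to surgery, then 30, which is 93 days. If onset were uniform over it, 28/93 = 30% would precede SRT. Earlier surgery raises that share.

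**The case against.** The strongest reply is that falling back to a regimen that passed its own run-in is a legitimate design choice, and that the plan is not without protection. Section 5.10 item 3 makes a hazardous incidence or severity of adverse drug reactions a ground for termination, worded as a consequence and not as an option. Appendix 5 obliges the Principal Investigator to notify the DSMC when grade 3 or 4 events exceed the brochure or label rate, and allows a voluntary hold. Section 6.3.4 adds monthly Site Committee review of grade 3 to 5 events with attribution. The 15% rule counts study-induced unfitness that leads to unresectability. All of this stands. What it does not supply is a numeric toxicity criterion for this step, or a requirement to examine pre-SRT events before the expansion opens.

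Three stronger readings are tempting, and the documents do not support them.

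- **That the plan always opens the expansion.** The provisions above can prevent it. Also, the Cohort 2 pass branch is joined by an or, so more than 33% toxicity with at most one unresectable patient literally also satisfies the route to "proceed to Expansion Cohort (randomization between parameters of Cohort 1 and Cohort 2". The two branches overlap.
- **That pembrolizumab alone would be over the protocol's own limit.** The limit is defined per six-patient cohort, and Cohort 1 must have met the run-in criteria for this branch to apply. Any excess appears only after pooling 12 patients, which the plan does not define, and 5/12 is imprecise.
- **That the trial would conclude SRT was the cause.** The branch allocates the next patients; it makes no causal statement.

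It is also fair that a pooled count has unequal windows: Cohort 1 is observed to 30 days after surgery, Cohort 2 SRT recipients only until SRT. The pooled figure is therefore a lower bound on pembrolizumab toxicity.

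**Conclusion.** The point holds in this form. As the adverse branch is written, Cohort 2 toxicity with onset before SRT, or in patients who never receive SRT, is pembrolizumab-alone experience that counts only against the combination. It then leads to a 28-patient pembrolizumab-alone expansion, although the same excess in Cohort 1 ends the study. This is a stated rule that can misdirect the next step, not merely a missing detail.

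Its size depends on two quantities the documents do not give for this setting: the true toxicity rate and the share of events before SRT. At 9.5%, with every event before SRT, the path has a probability of 0.2% to 0.5%. The 9% to 18% at a 40% rate is a worst case, because it also needs every event before SRT. A reader should not take it as the expected frequency. The path is rare if pembrolizumab is well tolerated. It matters more when pembrolizumab is not, which is the situation a safety run-in exists to detect.

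**What to change.** Reconcile the Cohort 1 and Cohort 2 branches in 2.1 and 2.2 with the attribution text in 5.2.1.1 and the termination criteria in 5.10. State that Cohort 2 toxicity with onset before SRT, and all toxicity in patients never given SRT, counts as pembrolizumab-alone experience and is assessed together with Cohort 1 before the pembrolizumab-alone expansion opens. The criterion and its consequence are for the sponsor to set. The same edit should remove the overlap between the pass and adverse branches. Report run-in toxicity by onset before or after SRT, and note that the pre-SRT count is a lower bound because later pembrolizumab events are left out.

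The text change is short and needs no new adverse event data: 6.4.8.4 already asks staff to "Record the start and stop dates of the adverse event". The statistical cost is a small added chance of pausing or stopping a tolerable regimen. If, for illustration, the existing 33% were applied to the 12 patients, that chance would be at most 0.5% at a 9.5% rate and 3.1% to 4.3% at 20%, with all Cohort 2 events before SRT.

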#### 3.2 Secondary Objectives & Hypotheses

(1) **Objective:** To assess the safety of preoperative pembrolizumab +/- SRT when combined with surgery;

**Hypothesis:** In patients scheduled for NSCLC resection, pembrolizumab, or pembrolizumab + SRT, given in the preoperative window, will meet safety criteria described by the protocol;

(2) **Objective:** To record the toxicity of preoperative pembrolizumab +/- SRT when combined with surgery, according to CTCAE v. 4, including immune-related adverse events (AEs);

**Hypothesis:** In patients scheduled for NSCLC resection, pembrolizumab, or pembrolizumab + SRT, given in the preoperative window, will result in acceptable short-term and perioperative toxicity;

(3) **Objective:** To determine the 1-year overall survival rate resulting from preoperative pembrolizumab +/- SRT when combined with surgery;

**Hypothesis:** In patients scheduled for NSCLC resection, pembrolizumab + SRT given in the preoperative window will result in a higher 1-year survival rate than pembrolizumab alone;

(4) **Objective:** To determine the 1-year relapse free survival rate resulting from preoperative pembrolizumab +/- SRT when combined with surgery;

**Hypothesis:** In patients scheduled for NSCLC resection, pembrolizumab + SRT given in the preoperative window will result in a higher 1-year relapse free survival rate than pembrolizumab alone;

(5) **Objective:** To determine the 1-year rate of distant metastases resulting from preoperative pembrolizumab +/- SRT when combined with surgery;

**Hypothesis:** In patients scheduled for NSCLC resection, pembrolizumab + SRT given in the preoperative window will result in a lower 1-year distant metastasis rate than pembrolizumab alone;

(6) **Objective:** To assess quality of life associated with preoperative pembrolizumab +/- SRT when combined with surgery;

**Hypothesis:** In patients scheduled for NSCLC resection, pembrolizumab, or pembrolizumab + SRT, given in the preoperative window, will result in acceptable short-term and perioperative quality of life;

(7) **Objective:** To determine the rate of unresectability that results from a program of preoperative pembrolizumab +/- SRT to be followed by a planned surgery;

**Hypothesis:** In patients scheduled for NSCLC resection, either pembrolizumab or pembrolizumab + SRT given in the preoperative window will both result in <15% overall rate of unresectability following the preoperative program;

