### **5.10 Clinical Criteria for Early Trial Termination**

Early trial termination will be the result of the criteria specified below:

1. Quality or quantity of data recording is inaccurate or incomplete
2. Poor adherence to protocol and regulatory requirements
3. Incidence or severity of adverse drug reaction in this or other studies indicates a potential health hazard to subjects
4. Plans to modify or discontinue the development of the study drug

In the event of Merck decision to no longer supply study drug, ample notification will be provided

so that appropriate adjustments to subject treatment can be made.

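### After the two six-patient run-ins, the protocol sets no pre-specified quantitative toxicity boundary for the 28-patient expansion

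*Combined protocol and SAP*

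**What the plan says.** Section 2.2 (Trial Diagram) sets a toxicity limit for each run-in cohort. Cohort 1 is described as "6 patients. The patients will undergo 2 cycles of pembrolizumab prior to surgery" and Cohort 2 as "6 patients. The patients will undergo 2 cycles of pembrolizumab then within the week". For Cohort 2 the adverse branch reads "If >33% of patients in Cohort 2 experience grade 3 immune-related toxicity attributable to study interventions", with toxicity determined within 30 days of surgery; Cohort 1 has the same limit. In both cohorts the toxicity condition is joined by "or" to a condition on unresectable patients.

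The expansion follows: "28 patients. The patients will be treated according to Cohort 1 if Cohort 2 failed to meet the specified safety milestones"; otherwise patients are randomised between the two regimens. No toxicity limit is attached. The Stopping Rule then covers all phases but concerns unresectability: "If at any point during the study, >15% of patients progress to unresectability over the course of the study treatment". Study-induced medical unfitness counts only when it makes the patient unresectable.

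Elsewhere, section 3.2 has the hypothesis that the regimens, "given in the preoperative window, will meet safety criteria described by the protocol", and section 4.4 identifies the criterion as at most 33% grade 3 immune-related toxicity. Section 5.10 lists as a ground for early termination "Incidence or severity of adverse drug reaction in this or other studies indicates a potential health hazard to subjects". Section 6.3.4 provides Site Committee and DSMC review. Appendix 5 (Review of Adverse Event Rates) requires a report to the DSMC if grade 3 or 4 events exceed the Investigator Brochure or package insert rate. Section 7 contains no toxicity monitoring rule.

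**The concern.** The protocol treats two harms differently. For unresectability it recognises that early data are thin and monitors cumulatively to the end. For toxicity it applies its numerical limit once per regimen, at six patients, and gives no number, denominator or look schedule after that. The expansion is 28 of 40 patients (70%).

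These patients are candidates for resection of stage I-IIIA disease. If a regimen's true toxicity rate exceeds the protocol's own limit and it passes the run-in by chance, the evidence accumulates in data already collected, but nothing says in advance how much of it prompts a pause. The decision then depends on judgement in an open-label trial.

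**Working it through.** **Inputs.** Run-in of 6 per regimen, limit of 33%, expansion of 28 (section 2.2). Permuted blocks of 4 with no ratio stated (section 5.3); I assume 1:1, so 14 further patients per regimen and 20 in total. If only Cohort 1 parameters continue, all 28 receive that regimen. The documents give no expected toxicity rate for these preoperative regimens, so the true rate p is an assumption shown over a range. The plan states no operating characteristics for the toxicity rule, so there is no figure of its own to reproduce.

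**Two readings of 33%.** Two events in six is 33.3%, literally above 33% but not above one third. I carry both: at most 1/6, or at most 2/6. Both take the toxicity limb alone, setting aside the "or".

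**Step 1: run-in pass probability.** P(pass) = sum of C(6,x) p^x (1-p)^(6-x) over the allowed x.

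- p = 40%: P(0) = 0.0467, P(1) = 0.1866, P(2) = 0.3110. At most 1: 0.233. At most 2: 0.544.
- p = 50%: at most 1: (1+6)/64 = 0.109. At most 2: (1+6+15)/64 = 0.344.

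At p = 40% the expected further patients with events are 14 × 0.40 = 5.6, or 28 × 0.40 = 11.2.

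**Step 2: carry the same limit forward.** Illustrative looks at 10 and 15 patients per regimen, crossing if the cumulative share exceeds one third: 4 or more of 10, or 6 or more of 15. Probabilities are conditional on passing the run-in.

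Worked case, p = 50%, at most 2/6 allowed. Given a pass, 0, 1 or 2 events have weights 1, 6 and 15 out of 22.

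- Look at 10: four more patients must bring the total to 4. The chances are 1/16, 5/16 and 11/16, giving (1×1 + 6×5 + 15×11)/(22×16) = 196/352 = 0.557.
- Look at 15: those continuing hold 3, 2 or 1 events with weights 100, 45 and 10 out of 352. They reach 6 with chances 16/32, 6/32 and 1/32, giving (1600 + 270 + 10)/11264 = 0.167.
- Total: 0.557 + 0.167 = 0.724.

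With at most 1/6 allowed, the same steps give 31/112 + 830/3584 = 0.277 + 0.232 = 0.508.

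| True rate | Run-in pass, at most 1/6 | Run-in pass, at most 2/6 | Crossing at 10 or 15 after a pass (1/6 reading to 2/6 reading) |
|---|---|---|---|
| 10% | 88.6% | 98.4% | 0.2% to 0.7% |
| 20% | 65.5% | 90.1% | 2.5% to 7.5% |
| 30% | 42.0% | 74.4% | 11% to 25% |
| 40% | 23.3% | 54.4% | 28% to 49% |
| 50% | 10.9% | 34.4% | 51% to 72% |

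Five of 15 is also 33.3%, so the ambiguity recurs at that look. The table counts only 6 or more of 15.

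**Step 3: outcome lag.** The table treats each outcome as known at the look. Cycle 2 is given at 3 weeks, surgery may follow up to 6 weeks after the last dose, and toxicity is determined to 30 days after surgery: 3 + 6 + about 4 = about 13 weeks for a full assessment. At 4 patients per month (section 7.2), or 2 per regimen under 1:1, about 2 × 3 = 6 more patients of a regimen could start in that time. Toxicity seen early, or surgery done sooner, shortens the lag.

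**The case against.** The strongest answer is that a safety run-in followed by a committee-supervised expansion is a legitimate design, and oversight continues. Section 5.10 permits termination for adverse-reaction incidence or severity. Appendix 5 has a benchmarked reporting duty. Its reference rate lies outside these documents, but the one comparable figure within them, 9.5% grade 3 or higher treatment-related events in the advanced-disease study in section 4.1.2, is well below 33%, so that report could come before a 33% boundary is crossed. Toxicity that prevents resection counts towards the 15% stop. The 40-50% scenarios are four to five times that 9.5%.

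Most of this stands. A reader might infer that an unsafe regimen would continue unchecked; the documents do not support that. Nor do they support the inference that the 33% criterion is not evaluated in the expansion, because section 4.4 keeps it as a secondary objective without restricting it to the run-ins. What is absent is a pre-specified interim boundary. The Appendix 5 route leads to a report, section 5.10 gives no number, and grade 3 toxicity that still permits surgery, or follows it, does not enter the 15% rule.

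A reader might also infer that checking after every patient would be better. On the same assumptions it would cross in 29-48% of passed regimens at a true 30%, against 11-25% for looks at 10 and 15. Any benefit is also reduced by outcome lag, and premature stopping would erode a primary analysis that needs 26 evaluable patients.

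**Conclusion.** The point holds as a gap in pre-specification, not as an absence of safety oversight. After the run-ins no quantitative toxicity boundary applies, and the run-in cannot reliably exclude a regimen above the protocol's own limit: the toxicity limb is met with probability 23% or 54% at a true 40%, and 11% or 34% at 50%, depending on how 2/6 is read. About 14 or 28 further patients may then be treated under unquantified or indirect safeguards.

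The pass probabilities rest on independent patients and assumed true rates; the documents do not suggest that 40-50% is expected. The 14 rests on 1:1 allocation. The crossing probabilities also assume no outcome lag, so fewer patients would be spared in practice than they suggest. An added rule brings a real chance of an unnecessary hold when the true rate is close to but within the limit. That is why a crossing should prompt a hold and review rather than automatic termination.

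**What to change.** Extend the Stopping Rule paragraph of section 2.2 so that the protocol's existing toxicity limit is also checked cumulatively, separately by regimen, at a few scheduled looks agreed with the DSMC (for example, 10 and 15 evaluable patients per regimen, run-in included). A crossing should trigger an accrual hold and DSMC review. Define evaluable for this purpose, given the replacement rule in section 5.9. Print the operating characteristics, including true rates of 20% and 30%, and state that they assume no outcome lag. If only Cohort 1 parameters continue, set looks for that longer series (6 + 28 = 34 patients).

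Within each run-in cohort, close enrolment once the limit can no longer be met. This leaves the run-in decision unchanged and only brings it forward. It requires the sponsor first to reconcile section 2.2: with "or" in both branches, a cohort above 33% toxicity with at most one unresectable patient satisfies both, and 2/6 may fall on either side of 33%. Whether grade 4-5 events count should also be made explicit.

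The cost is an amended paragraph and some statistical work. Grade 3 and higher events are already recorded and reviewed, so no new data are needed. The operational price is possible pauses in accrual and, near the limit, holds that prove unnecessary.
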